6.3 Missing Data Imputation

Missing Data Imputation for SVR

HCV RNA values will be selected for analysis based on the analysis windows defined in Section 6.2.

For analyses of SVR, subjects missing visit values will have backward imputation applied, if possible. For backward imputation, if the nearest HCV RNA value after the SVR window is unquantifiable or undetectable, then it will be used to impute the HCV RNA value in the SVR window. If a subject is missing an HCV RNA value within the appropriate SVR window after performing backward imputation, then this value will be imputed with an HCV RNA value from a local laboratory if present; otherwise, the HCV RNA value will be missing. A subject with missing HCV RNA data in the analysis window, after imputations, will be imputed as a failure.

Regardless of the imputation method described above, if a subject starts another treatment for HCV, then all HCV RNA values for this subject measured on or after the start date of the new HCV treatment will be excluded from analyses. The subject will be considered a failure for summaries of viral response at all time points after the start of the new HCV treatment.

Missing Data Imputation for Virologic Failure

If HCV RNA values from the central laboratory are missing but a local laboratory value is present in the appropriate time period, then the local laboratory value will be used to assess PT relapse and on-treatment virologic failure.

Missing Data Imputation for PRO Questionnaires

The handling of missing data for patient reported outcomes (PROs) will be as follows. The missing items of the FSS questionnaire will be imputed with the average score of the answered items as long as more than 50% of the items on the FSS are answered. For EQ-5D-3L index and VAS scores, no imputation will be performed for missing items.

If a subject starts another treatment for HCV, then all PRO assessment values for this subject measured on or after the start date of the new HCV treatment will be excluded from analyses.

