5.1.2 Modified Intention-to-Treat (mITT) Populations

Sensitivity analyses of SVR₁₂ as described in Section 10.5, when applicable, will be performed on the ITT population modified to exclude subjects who have multiple GTs according to the central laboratory or phylogenetic analyses of the baseline sample or subjects who received an incorrect duration of treatment due to incorrect classification of

GT or treatment experience at randomization (mITT-GT), and on the mITT-GT population modified to exclude subjects who did not achieve SVR₁₂ for reasons other than virologic failure (i.e., subjects with reasons other than on-treatment HCV virologic failure and relapse) (mITT-GT-VF).

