On-treatment HCV virologic failure = **Breakthrough** or **EOT failure**; if a subject meets both definitions of **Breakthrough** and **EOT failure**, he or she will be categorized as **Breakthrough** only.

SVR₄ = HCV RNA < LLOQ in the SVR₄ window (4 weeks after the last actual dose of active study drug) without any confirmed quantifiable (\geq LLOQ) post-treatment value before or during that SVR window.

SVR₁₂ = HCV RNA < LLOQ in the SVR₁₂ window (12 weeks after the last actual dose of active study drug) without any confirmed quantifiable (\geq LLOQ) post-treatment value before or during that SVR window.

SVR₂₄ = HCV RNA < LLOQ in the SVR₂₄ window (24 weeks after the last actual dose of active study drug) without any confirmed quantifiable (\geq LLOQ) post-treatment value before or during that SVR window.

Relapse₁₂ = confirmed HCV RNA \geq LLOQ between end of treatment and 12 weeks after last actual dose of active study drug (up to and including the SVR₁₂ assessment time point) for a subject with HCV RNA < LLOQ at Final Treatment Visit who completed treatment and has post-treatment HCV RNA data available, excluding reinfection as described below.

Relapse₂₄ = confirmed HCV RNA \geq LLOQ within the SVR₂₄ window for a subject who achieved SVR₁₂ and has HCV RNA data available in the SVR₂₄ window, excluding reinfection.

Relapse_{overall} = confirmed HCV RNA \geq LLOQ between end of treatment and up to and including the last HCV RNA measurement collected in the PT Period for a subject with HCV RNA < LLOQ at Final Treatment Visit who completed treatment and has post treatment HCV RNA data available, excluding reinfection.

Only subjects who have at least one post-treatment HCV RNA value will be included in analyses of relapse. For the analyses of relapse, completion of treatment is defined as a study drug duration of 52 days or greater for subjects assigned to 8 weeks of treatment and 105 days or greater for subjects assigned to 16 weeks of treatment. If the last available post-treatment value is \geq LLOQ, then the subject will be considered a relapse (i.e., will not require confirmation).

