HCV reinfection is defined as confirmed HCV RNA \geq LLOQ after the end of active treatment in a subject who had HCV RNA $<$ LLOQ at Final Treatment Visit, along with the post treatment detection of a different HCV genotype, subtype, or clade compared with baseline, as determined by phylogenetic analysis of the NS3 or NS5A, and/or NS5B gene sequences. Reinfection in the case of the same HCV subtype is defined as a clade switch, as indicated by the lack of clustering between the baseline and post-treatment sequences by phylogenetic analysis. If phylogenetic analysis is not possible due to technical difficulties, HCV reinfection may be determined with a confirmed HCV genotype or subgenotype switch by the Versant HCV Genotype Inno-LiPA Assay v2.0 or Sanger assay.

Post-treatment relapse is defined as described earlier (**Relapse₁₂**, **Relapse₂₄**, **Relapse_{overall}**), and no genotype, subtype, or clade switch compared with baseline as determined by phylogenetic analysis of the NS3 or NS5A gene sequences. If phylogenetic analysis is not possible due to technical difficulties, the subject will be defined as having a post-treatment relapse unless an HCV genotype or subgenotype switch is confirmed by the Versant HCV Genotype Inno-LiPA Assay v2.0 or Sanger assay.

Reasons for SVR₁₂ Non-Response

Subjects who do not achieve SVR₁₂ (SVR₁₂ non-responders) will be categorized as having:

1. On-treatment HCV virologic failure (see **On-treatment HCV virologic failure** definition; if a subject meets both definitions of **Breakthrough** and **EOT failure**, he or she will be categorized as **Breakthrough** only);
2. Relapse₁₂;
3. Prematurely discontinued study drug with no on-treatment virologic failure (defined as any SVR₁₂ non-responder who prematurely discontinued study drug [study drug duration $<$ 52 days for subjects assigned to 8 weeks of treatment, and

- < 105 days for subjects assigned to 16 weeks of treatment] and did not meet the **On-treatment HCV virologic failure** definition);
4. HCV reinfection (see definition described earlier);
 5. Missing follow-up data in the SVR₁₂ window (defined as any subject who completed study drug without data in the SVR₁₂ window after applying the imputation rules and not meeting the definitions of [1], [2], [3], or [4]);
 6. Other (defined as any SVR₁₂ non-responder not meeting the definitions of [1] – [5]).

Reasons for SVR₂₄ Non-Response

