10.5.1 Imputation Approaches

In addition to imputing SVR₁₂ as described in Section 6.3, SVR₁₂ will be presented for the overall set of Arm A subjects and the Arm A subjects in each of the GT1-infected and GT2-infected groups in the ITT population using the following other methods to impute missing HCV RNA values:

- impute any missing HCV RNA values in the SVR₁₂ window by carrying forward the last non-missing (post-baseline) HCV RNA value prior to the SVR₁₂ window;
- impute as described in Section 6.3 but treat SVR₁₂ non-responders who were categorized as "prematurely discontinued study drug with no on-treatment virologic failure" or "missing follow-up data in the SVR₁₂ window" as successes.

For each of these, the number and percentage of Arm A subjects with SVR₁₂ will be presented along with two-sided 95% CIs using both the normal approximation to the binomial distribution and the Wilson score method. Within the 3 groups of subjects specified above, these analyses will also be performed for the geographic region of China.

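### A completer with an empty SVR12 window and later viraemia is labelled missing, dropped from mITT-GT-VF and scored a success in a sensitivity analysis

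*SAP*

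**What the plan says.** - **Imputation (SAP 6.3).** When the SVR window is empty, "if the nearest HCV RNA value after the SVR window is unquantifiable or undetectable, then it will be used to impute" the window value. Failing that, a local laboratory value is used. After that, "A subject with missing HCV RNA data in the analysis window, after imputations, will be imputed as a failure". Nothing is said about a later value at or above LLOQ. Protocol 8.1 announces a backward method but gives no direction.
- **Windows (SAP Table 6).** SVR12 covers Days 57–126 after the last active dose. The PT Week 24 visit window opens on Day 127.
- **Relapse (SAP 10.1).** Relapse12 runs "between end of treatment and 12 weeks after last actual dose of active study drug", "up to and including the SVR₁₂ assessment time point". Relapse24 is a confirmed quantifiable value "within the SVR₂₄ window for a subject who achieved SVR₁₂ and has HCV RNA data available" there. Relapse_overall has neither limit.
- **Reason for non-response (SAP 10.1).** Reason 5, missing follow-up, is "defined as any subject who completed study drug without data in the" SVR12 window after imputation who fits none of reasons 1–4.
- **mITT-GT-VF (SAP 5.1.2).** This set drops subjects who missed SVR12 "for reasons other than virologic failure (i.e., subjects with reasons other than on-treatment HCV virologic failure and relapse").
- **Second sensitivity method (SAP 10.5.1).** The instruction is to "impute as described in Section 6.3 but treat" reasons 3 and 5 as successes.

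**The concern.** Each rule is reasonable alone, but together they leave a gap. A subject whose relapse is first seen after an empty SVR12 window has a known virologic outcome, yet the SAP handles that subject as if the outcome were unknown. The subject then leaves the population meant to isolate virologic failure, and a sensitivity analysis of the primary endpoint counts a cure despite documented viraemia.

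The outputs at stake are the relapse secondary endpoint, the table of reasons for non-response, mITT-GT-VF and the 10.5.1 analyses. mITT-GT-VF also feeds the stepwise logistic model in SAP 10.6 and the comparisons of SVR12 by baseline polymorphism in 10.8 (Analyses 2 and 3). All of these rest on very few virologic failures.

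**Working it through.** **1. The subject.** Completed treatment; HCV RNA < LLOQ at the Final Treatment Visit; PT Week 4 < LLOQ or missing; no central or local value in Days 57–126; HCV RNA ≥ LLOQ from Day 127 on; no new HCV treatment; not reinfection.

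**2. The rules applied in turn.**

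| Output | Result | Why |
|---|---|---|
| Primary SVR12 | Failure | Window still empty after imputation (6.3) |
| SVR12 reason | 5, missing follow-up | Not on-treatment failure, Relapse12, premature stop or reinfection |
| Relapse12 | In denominator, not a relapse | Has a post-treatment value, but the positive one falls after the time limit |
| Relapse24 | Not eligible | SVR12 not achieved |
| SVR24 reason (positive on Days 127–210) | 7, other | Fits none of reasons 1–6 |
| Relapse_overall | Relapse | No time limit, no SVR12 condition |
| mITT-GT-VF | Removed | Reason 5 is not virologic failure |
| 10.5.1, second method | Success | Reason 5 recoded |
| 10.5.1, carry-forward | Success | Last value before the window is < LLOQ (PT Week 4 or, if that is missing, the last on-treatment value) |

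If PT Week 4 is quantifiable and the next available value is too, the subject is a Relapse12 case and the gap does not arise.

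**3. How often.** The plan gives no figure, so this uses the protocol's relapse data (Tables 5 and 7, non-cirrhotic, planned durations) and the Table 11 genotype weights.
- GT1: 0/384, so 0.
- GT2: 126 × 2/195 = 1.29.
- GT3: 7% × 336 = 23.5 subjects. At 5/178 (treatment-naïve, 8 weeks) this gives 0.66; at 1/22 (treatment-experienced, 16 weeks) it gives 1.07.
- GT4–6: 0/57, so 0.
- Total in Arm A: 1.95 to 2.36 relapses, or 0.58% to 0.70% of 336.

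Assume 1–2% of Arm A (3.36 to 6.72 subjects) miss PT Week 12 but return later, independently of relapse. The expected number in the gap is 3.36 × 0.0058 = 0.02 to 6.72 × 0.0070 = 0.05. This ignores the further requirement that PT Week 4 did not already show the relapse.

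**4. Size per subject, if one occurs.**
- Second method of 10.5.1: 1/336 = 0.30 points overall, 1/170 = 0.59 in GT1, 1/126 = 0.79 in GT2.
- Relapse12, if there is no other relapse and all subjects are evaluable: 0% as written against 0.3% overall or 0.8% in GT2 with the subject counted.
- Relapse count: with about two other relapses, two are reported where three occurred.
- mITT-GT-VF, if this is the only virologic failure: 100% as written against 335/336 = 99.7% overall, or 125/126 = 99.2% in GT2.

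**5. Effect on the success criterion.** The lower bound is p − 1.96 × √(p(1 − p)/n).
- GT2 at the design rate: 121/126 gives 92.6% and 122/126 gives 93.8%. Both exceed 89%.
- At the boundary, one recoded subject can flip a sensitivity result: GT2 117/126 (88.4%) to 118/126 (89.4%) against 89%; GT1 160/170 (90.6%) to 161/170 (91.3%) against 91%; overall 311/336 (89.7%) to 312/336 (90.1%) against 90%.

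**The case against.** The case for leaving the text alone is substantial.

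- **The primary test is untouched.** A reader might infer that one-sided imputation inflates the primary SVR12 through these subjects. It does not: the viraemic subject is a failure whether or not the late value is used.
- **The asymmetry has a logic.** HCV RNA < LLOQ at PT Week 24 supports < LLOQ at Week 12. A positive at PT Week 24 does not show viraemia by Week 12, because it may be a later relapse. A reader might conclude that 6.3 should carry bad values back and count them as Relapse12. That would depart from Protocol 8.1.2.2, which limits relapse to 12 weeks after the last dose.
- **The event is not lost.** A reader might infer that it disappears from the report. In fact, Relapse_overall captures it, and SAP 10.7 lists it by subject and window. SAP 10.8 also provides for sequencing some such subjects.
- **It is rare and late.** SAP 4.4 limits the primary analysis to Arm A data through PT Week 12, so the conflict arises mainly afterwards. The three relapses whose timing the protocol's Introduction gives, under various regimens, were all at PT Week 4.
- **The affected analyses are favourable by design.**

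The first four stand and set the limits of the point. The last does not answer it: treating an unknown outcome as success is a legitimate extreme scenario, but this outcome is known. Likewise, mITT-GT-VF is meant to remove non-virologic failures, and this is a virologic one.

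Two passages in 10.1 might be cited as closing the gap. One says that a last available value ≥ LLOQ counts as relapse, but its own gloss shows that it only waives confirmation. The other lists Relapse_overall under post-treatment relapse, but the SVR12 reasons name only Relapse12. That mismatch is itself a reason to clarify the text.

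**Conclusion.** The point holds as a classification fault, not as a bias in the primary analysis. As written, the SAP labels documented viraemia as missing data, counts it as a non-relapse in Relapse12, removes it from mITT-GT-VF as non-virologic, and scores it as a success in 10.5.1.

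The size is small: well under one expected subject, given the assumed 1–2% who miss PT Week 12 but return and independence of that from relapse. Each such subject moves the sensitivity SVR12 by 0.3 points overall or 0.8 in GT2. No primary verdict changes, and at the GT2 design rate the sensitivity conclusion does not change either. A change is still worthwhile because the rule is wrong for the subjects it reaches, relapse counts are expected to be about two, and the correction is cheap.

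The same one-sidedness could be pursued into the Relapse24 denominator and into values after Day 210. With PT Week 24 nominally on Day 168, those cases are marginal and need no change.

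**What to change.** 1. **SAP 10.1, reasons for non-response.** Take out of reason 5 any completer whose nearest value after an empty SVR12 window is ≥ LLOQ, with no new HCV treatment and no reinfection. Give these subjects their own virologic-failure reason, such as relapse first documented after an empty SVR12 window.
2. **SAP 5.1.2.** Keep them in mITT-GT-VF as virologic failures.
3. **SAP 10.5.1.** Do not score them as successes under either method.
4. **SAP 10.4.** Leave Relapse12 at the protocol's 12-week limit and add a supplementary relapse count that includes them.
5. **SAP 10.1, last-available-value sentence.** State that it waives confirmation only and does not extend any relapse time limit.

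SAP 6.3 itself can stay as it is. The cost is a few lines of SAP text and derivation code, one more non-response category, and a slightly less favourable sensitivity result if such a subject occurs.

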7.0 Demographics, Baseline Characteristics, Medical History, and Other Medications

The safety population (and ITT population if it differs from the safety population) will be used to summarize demographics and baseline characteristics by treatment arm (Arm A and Arm B) and across the treatment arms for the set of all subjects, for each of the GT1-infected and GT2-infected groups, and for the geographic region of China during the DB Treatment Period. In addition, demographics and baseline characteristics will be summarized for the geographic region of China for each of the GT1-infected and GT2-infected groups.

The safety population will be used to summarize medical history and previous, concomitant, and PT medications by treatment arm and across the treatment arms for the set of all subjects and for the geographic region of China.

7.1 Demographic and Baseline Characteristics

Categorical demographic and baseline characteristic variables will be summarized with the number and percentage of subjects in each category and proportions will be compared between the treatment arms with a chi-square test. Continuous variables will be summarized with descriptive statistics (number of non-missing observations, mean, standard deviation, median, maximum and minimum), and means will be compared between the treatment arms with a one-way analysis of variance (ANOVA).

Continuous demographic variables include age, weight, height, waist circumference, and body mass index (BMI). Categorical demographic variables include sex, age category (< 65 or ≥ 65 years; < 75 or ≥ 75 years), BMI category (< 25, ≥ 25 to < 30, or ≥ 30 kg/m²), race, ethnicity, type of Asian descent (Chinese, Korean, Malay or Other), and geographic region.

Continuous baseline characteristics include baseline log₁₀ HCV RNA level, homeostasis model of assessment – insulin resistance (HOMA-IR), platelet count, albumin, GGT, LDL, HDL, total insulin, APRI, FIB-4, AST, ALT, AST/ALT ratio, creatinine clearance

(by Cockcroft-Gault formula, defined below), eGFR (using the modification of diet in renal disease [MDRD] formula modified for the Chinese population [C-MDRD], defined below), total, direct, and indirect bilirubin, total international normalized ratio (INR).

Categorical baseline characteristics include:

- HCV genotype (1, 2, 3, 4, 5, or 6) and available subtype (as determined by the central laboratory);
- HCV genotype (1, 2, 3, 4, 5, or 6) and available subtype (final HCV genotype and subtype as defined in Section 10.8);
- Prior HCV treatment history (naïve or experienced);
- HCV genotype (1, 2, 3, 4, 5, or 6) (as determined by the central laboratory) and prior HCV treatment history;
- HCV genotype (final HCV genotype as defined in Section 10.8) and prior HCV treatment history;
- For treatment-experienced subjects, type of prior treatment experience (IFN-based or SOF-based; subjects who received SOF will be categorized as SOF-based);
- For treatment-experienced subjects, type of non-response to previous treatment (on-treatment nonresponder or breakthrough, post-treatment relapse, or unknown/other);
- Screening HIV co-infection status (HCV mono-infected or HCV/HIV co-infected);
- IL28B genotype (CC, CT, or TT; CC or non-CC);
- Baseline HCV RNA level ($< 1,000,000$ or $\geq 1,000,000$ IU/mL; $< 6,000,000$ or $\geq 6,000,000$ IU/mL; $< 10,000,000$ or $\geq 10,000,000$ IU/mL);
- Baseline HOMA-IR (< 2 or ≥ 2 mU \times mmol/L²);
- Baseline fibrosis stage (equivalent to Metavir F0 – F1, F2, F3, F4 [if applicable]);
- Baseline platelet count (< 100 or $\geq 100 \times 10^9$ /L);
- Baseline albumin (< 35 or ≥ 35 g/L);

- Baseline creatinine clearance (Cockcroft-Gault) (< 60 , ≥ 60 to < 90 , or ≥ 90 mL/min);
- Baseline eGFR (C-MDRD) (< 60 , ≥ 60 to < 90 , or ≥ 90 mL/min/1.73 m²);
- Baseline total bilirubin (< 34.2 or ≥ 34.2 umol/L);
- Baseline total INR (continuous and < 1.7 or ≥ 1.7);
- History of diabetes (yes/no);
- History of bleeding disorders (yes/no);
- History of depression or bipolar disorder (yes/no);
- History of cardiovascular disease (yes/no);
- Baseline metabolic syndrome (yes/no);
- Injection drug use (yes, within last 12 months; yes, more than 12 months ago; or no);
- Baseline stable opiate substitution use (yes/no);
- Baseline hepato-protectant medication use (as determined by investigator on concomitant medication eCRF, yes/no);
- Tobacco use (user, ex-user, or non-user);
- Alcohol use (drinker, ex-drinker, or non-drinker);
- Concomitant use of Proton Pump Inhibitors (PPIs) (yes/no).

The demographic and baseline characteristics specified above, along with the following, will be summarized for subjects with HCV/HIV co-infection at Screening for the overall safety population and for the geographic region of China:

- HIV-1 treatment status (antiretroviral therapy [ART]-Naïve, ART-Treated),
- HIV-1 ART regimen (e.g., raltegravir [RAL], dolutegravir [DTG], rilpivirine [RPV]) for those receiving ART (as determined by investigator on concomitant medication eCRF) at baseline,
- Baseline CD4+ T-cell count (continuous; and < 200 , 200 to < 350 , 350 to < 500 , or ≥ 500 cells/mm³).

Any concomitant medication coded to the WHO Drug Dictionary ATC code of A02BC will be counted as a PPI.

If the IL28B genotype result is not available from a sample collected during the Screening period, then a result available from a sample collected at any time during the study will be used to summarize IL28B genotype.

HOMA-IR is defined as fasting glucose (mmol/L) \times fasting insulin (μ IU/mL) \div 22.5. Subjects who do not have concurrent fasting glucose and fasting insulin values at baseline will be excluded from the summary of baseline HOMA-IR.

Baseline fibrosis stage is defined for subjects with non-missing liver biopsy scores, FibroScan scores, or FibroTest scores. Only one score will be used to categorize each subject even if a subject has more than one score recorded. If a biopsy score is present, then it will be used to categorize the subject, regardless of the FibroScan/FibroTest score. Similarly, if a FibroScan score is present along with a FibroTest score, then the FibroScan score will be used to categorize the subject. If biopsy and FibroScan scores are not present and more than one FibroTest result is available, then the baseline FibroTest result (i.e., last non-missing FibroTest result on or before DB Day 1) will be used to categorize the subject. Subjects will be categorized as F0 – F1, F2, F3 or F4 according to [Table 11](#).

All subjects in this study will be categorized as not having cirrhosis (cirrhosis = no) since this study excludes subjects with cirrhosis.

Table 11. Baseline Fibrosis Stage

Baseline Fibrosis Stage, Metavir Equivalents	Liver Biopsy Metavir, Batts Ludwig, Knodell, IASL, Scheuer, or Laennec Score	Liver Biopsy Ishak Score	FibroScan (kPa)	FibroTest
F0 – F1	0 or 1	0, 1, or 2	< 8.8	\leq 0.48
F2	2	3	\geq 8.8 to < 9.6	0.49 to 0.58
F3	3	4	\geq 9.6 to < 14.6	0.59 to 0.72
F4	4	\geq 5	\geq 14.6	\geq 0.73

Baseline APRI and FIB-4 are calculated by the equations below. Subjects who do not have concurrent AST and platelet values at baseline will be excluded from the summary of baseline APRI. Age is defined in years at baseline. Subjects who do not have concurrent values of AST, ALT and platelet count at baseline or subjects who are missing age will be excluded from the summary of FIB-4.

$$\text{APRI} = \frac{\frac{\text{AST Level (U/L)}}{\text{AST (Upper Limit of Normal)(U/L)}}}{\text{Platelet Count (10}^9\text{/L)}} \times 100$$

$$\text{FIB-4} = \frac{\text{Age (years)} \times \text{AST Level (U/L)}}{\text{Platelet Count (10}^9\text{/L)} \times \sqrt{\text{ALT (U/L)}}}$$

The central laboratory calculates the estimated creatinine clearance (CrCl) based on the following Cockcroft-Gault formula:

$$\text{CrCl (mL/min)} = [(140 - \text{age}) \times (\text{weight in kg}) \times (0.85 \text{ if female})] / [\text{serum creatinine (mg/dL)} \times 72].$$

The central laboratory calculates eGFR by C-MDRD using the following equation, where serum creatinine is measured in mg/dL and age is measured in years:

$$\text{eGFR (mL/min/1.73 m}^2\text{)} = 175 \times (\text{Serum Creatinine})^{-1.234} \times (\text{Age})^{-0.179} \times (0.79 \text{ if female}).$$

Subjects will be classified as having metabolic syndrome if at least 3 of the 5 characteristics in [Table 12](#) are present.

Table 12. Clinical Identification of Metabolic Syndrome

Risk Factor	Defining Level in Conventional Units	Defining Level in SI Units
Abdominal obesity, given as waist circumference		
Men	> 40 in	> 102 cm
Women	> 35 in	> 88 cm
Triglycerides	≥ 150 mg/dL	≥ 1.695 mmol/L
HDL cholesterol		
Men	< 40 mg/dL	< 1.03452 mmol/L
Women	< 50 mg/dL	< 1.29315 mmol/L
Blood pressure (BP)	Systolic BP ≥ 130 mm Hg or Diastolic BP ≥ 85 mm Hg	
Fasting glucose	≥ 100 mg/dL	≥ 5.5507 mmol/L

Cross reference: Grundy 2004⁶

Medical history data will be coded using the Medical Dictionary for Regulatory Activities (MedDRA); the actual version of the MedDRA coding dictionary will be noted in the clinical study report. Histories of diabetes, bleeding disorders, depression or bipolar disorder, and cardiovascular disease will be defined by a subject having medical history coded to at least 1 preferred term within any of the high level terms specified for the category in [Table 13](#).

Table 13. Medical History Categories

Category	MedDRA High Level Term Name
Diabetes	Diabetic complications cardiovascular Diabetic complications dermal Diabetic complications gastrointestinal Diabetic complications NEC Diabetic complications neurological Diabetic complications ophthalmic Diabetic complications renal Diabetes mellitus (incl subtypes) Hyperglycaemic conditions NEC
Bleeding disorders	Coagulation factor deficiencies Coagulopathies Platelet disorders NEC Thrombocytopenias Coagulation disorders congenital
Depression or bipolar disorder	Depressive disorders Bipolar disorders Mood alterations with manic symptoms

Table 13. Medical History Categories (Continued)

Category	MedDRA High Level Term Name
Cardiovascular disease	Coronary artery disorders NEC
	Ischaemic coronary artery disorders
	Cardiac conduction disorders
	Rate and rhythm disorders NEC
	Supraventricular arrhythmias
	Ventricular arrhythmias and cardiac arrest
	Congenital cardiac malpositions and transpositions
	Congenital cardiac structural defects NEC
	Congenital cardiovascular disorders NEC
	Cardiac disorders congenital NEC
	Cardiac hypoplasias congenital
	Cardiac malpositions congenital
	Cardiac septal defects congenital
	Cardiac valve disorders congenital
	Cardiovascular disorders congenital NEC
	Great vessel disorders congenital
	Multiple cardiac abnormalities congenital
	Persistent foetal circulation disorders
	Heart failure signs and symptoms
	Heart failures NEC
	Left ventricular failures
	Right ventricular failures
	Accelerated and malignant hypertension
	Renal hypertensions
	Vascular hypertensive disorders NEC
	Coronary necrosis and vascular insufficiency
	Infectious myocarditis
	Noninfectious myocarditis
	Peripheral vasoconstriction, necrosis and vascular insufficiency
	Aortic valvular disorders
	Cardiac valve disorders NEC
	Mitral valvular disorders
	Pulmonary valvular disorders
	Tricuspid valvular disorders
Aortic inflammatory disorders	
Arterial inflammations	
Vasculitides NEC	

